**STUDY SYNOPSIS**

**Research Questions:**

1. Among patients with metastatic solid tumours in each of three pre-defined cohorts (A, B, C), what proportion of patients have a positive cytology, a positive circulating tumour DNA (ctDNA), and/or positive circulating tumour cells (CTC) in cerebrospinal fluid (CSF) samples?
2. Among the patients enrolled in the study, how do ctDNA and CTC results obtained from cerebral spinal fluid (CSF) and plasma compare in each of three cohorts (A, B, C)?
3. Is it feasible to perform proteomic analysis of CSF among patients with metastatic solid tumours who have at least one positive CSF biomarker (cytology and/or ctDNA and/or CTCs) in each of three cohorts (A, B, C)?

**Population:**

**Inclusion Criteria:**

1. Age > 18.
2. Diagnosed with a metastatic solid tumour in one of the following scenarios:
  - a. Patients in Cohort A will have leptomeningeal metastatic disease (LMD) with or without parenchymal brain metastases.
  - b. Patients in Cohort B will have parenchymal brain metastases but no evidence of LMD.
  - c. Patients in Cohort C will have metastatic solid tumours no CNS metastases (i.e. no LMD nor brain metastases).
3. Patient is suitable for lumbar puncture and/or has an Ommaya reservoir that is accessible for CSF collection.
4. Patient is eligible at any time point in their treatment whether they have started treatment for LMD
5. Patients who previously enrolled in the study but for whom CSF biomarkers were negative can re-enroll later (e.g. upon progression of disease in the CNS).

**Exclusion Criteria:**

1. Inability to understand and not willing to sign a written informed consent document (language barrier not excluded; patients can have translator).

**Intervention:** One-time CSF collective via lumbar puncture or Ommaya reservoir and collection of concurrent plasma of peripheral blood (liquid biopsy).

**Comparison:** Not applicable.

**End points:**

1. Primary endpoint: Proportion of eligible patients with positive CSF cytology, positive ctDNA, and positive CTCs.
2. Secondary endpoint: Concordance of mutations identified on CSF ctDNA with plasma ctDNA.
3. 3. Exploratory endpoint: Feasibility of conducting proteomic analysis of CSF.

**Study Design:**

Prospective single centre feasibility trial conducted at the Sunnybrook Odette Cancer Centre (SOCC).

- Cohort A: 20 patients with any malignant solid tumour with LMD either suspected on imaging and/or confirmed via CSF cytology will be recruited.
- Cohort B: 20 patients with any malignant solid tumour with parenchymal brain metastases will be recruited.
- Cohort C: 20 patients with metastatic solid tumours and no evidence of LMD or parenchymal brain metastases (control group) will be recruited.

**Time Target:**

Patients will be recruited over a 12-month time period.

**1. OBJECTIVES**

**Primary Objectives**

To estimate the proportion of patients with solid tumours and CNS metastases (either meeting criteria for Cohort A or B), or no CNS metastases (Cohort C) who have positive CSF cytology, positive ctDNA, and/or positive CTCs

**Secondary Objectives**

1. The concordance of mutations identified based on ctDNA profiling in the CSF and blood plasma in each of three cohorts (A, B, C).
2. To explore the feasibility of proteomic analysis using CSF samples in each of three cohorts (A, B, C).

## 2. BACKGROUND

Leptomeningeal metastatic disease (LMD) is the spread of malignant cells into the pia and arachnoid mater of the brain and spinal cord, affecting approximately 5-8% of all solid tumour types. It is a rare complication that is associated with a high symptom burden and poor prognosis, with median survival ranging from 6-8 weeks without treatment and 3-6 months with treatment. Common solid tumours that result in LMD include breast, lung, gastro-intestinal (GI), melanoma, and primary central nervous system (CNS) cancers. Resulting from the infiltration of cancer cells into the CNS, LMD can present with various symptoms such as headache, seizures, visual disturbances, weakness, and confusion. The diagnosis and monitoring of LMD remain challenging due to the nonspecific clinical symptoms and false negative rates for MRI imaging and cerebrospinal fluid (CSF) analysis.

Current research states that CSF analysis is the gold standard for diagnosing LMD, however circulating tumour cells (CTCs) and circulating tumour DNA (ctDNA) are new alternative diagnostic methods that have not been thoroughly evaluated to-date. In this study, CSF samples collected via lumbar puncture (LP) or an Ommaya reservoir, along with blood plasma, will be obtained from patients with solid tumours who have diagnosed or suspected LMD. These samples will be analyzed for biomarkers to explore their association with clinical outcomes and potential therapeutic targets, ultimately guiding more effective treatment strategies.

In addition, there is an unmet need to identify biomarkers in the CSF among patients with and without parenchymal brain metastases, even with the absences of LMD. If our exploratory study is successful, we may identify a novel mechanism to understand targetable mutations of CNS metastases through relatively less invasive mechanisms than craniotomy to surgically resect brain metastases.

## 3. STUDY DESIGN

### Cohort A

20 patients with any malignant solid tumour with LMD either suspected on imaging and/or confirmed via CSF cytology will be recruited with or without brain metastases.

### Cohort B

20 patients with any malignant solid tumour and parenchymal brain metastases without evidence of LMD will be recruited.

### Cohort C

20 patients with any malignant solid tumour and no evidence of CNS involvement (no LMD or parenchymal brain metastases) will be recruited as a control group.

[figure not shown]

Figure 1: Study Schema

#### 4. ENROLLMENT PROCEDURES

##### Patient Enrollment

Patients will be screened for eligibility to participate in the study. The study team will inform the treating oncologist regarding their eligibility prior to their medical appointment. After the study is introduced to eligible patients by their oncologist, the study will be discussed in more detail by the study team to obtain informed consent.

#### 5. PLANNED DATA COLLECTION

##### Planned CSF and Blood Plasma Collection:

*CSF collection:* Using standard techniques, CSF samples of 15-20 cc will be collected via lumbar puncture (LP) or an Ommaya reservoir. For LP's, the use of a 20-gauge spinal needle and 2% lidocaine anaesthesia at L3/L4 or L4/L5 intervertebral disc space, with the patient in the lateral decubitus position. For ventricular reservoirs such as the Ommaya, a 25-gauge butterfly needle will be used without anaesthesia, and the first 2 mL of CSF collected will be discarded. Due to the fast clearance of tumour cells after sampling, analysis must be performed rapidly by a cytologist.

*Blood plasma collection:* Blood samples will be drawn into Streck Tubes. Two 10 mL vials of blood will be drawn per participant, gently mixed, and stored upright at 4°C until processing. Processing should occur within four hours of collection. Samples will be centrifuged at 1500 g for 10 minutes at 4°C using a sealed swinging bucket rotor to separate the plasma. Plasma will then be carefully extracted with a pipette set to 900 µL into 1.8 mL aliquots in 2 mL labelled microcentrifuge tubes and placed on ice. A second high-speed centrifugation at 10,000 rpm will be used to remove residual cellular debris. The buffy coat layer will be isolated and stored separately, and any remaining plasma will be used to resuspend the cellular pellet. Compatible plasma samples will be pooled, aliquoted, and stored at -80°C, alongside the buffy coat and pellet. All samples will be clearly labelled and handled under appropriate biosafety and waste disposal protocols.

## 6. BIOMARKER

### **Biomarker Plan**

This study involves the assessment of several biomarkers (cytology, ctDNA, CTCs, proteomics) in the blood and CSF of participants. These analyses will be performed at Sunnybrook and through collaborations with external centres/companies once appropriate material and data transfer agreements are obtained.

## 7. STATISTICAL ANALYSIS

### **Planned Cytological Analysis:**

CSF and blood plasma samples will undergo proteomic and cytological analysis using the genomic equipment at the Sunnybrook Research Institute (SRI). While the specific platform has yet to be finalized, technologies such as Next Generation Sequencing (NGS), the QX200 Droplet Digital PCR System, and ANGLE plc's Parsortix® system are under consideration for their suitability in cytological and proteomic applications.

### **Planned Statistical Analysis:**

For the first objective, binary data will be analyzed to determine the proportion of positive CSF samples from the total number of samples collected. These proportions will then be stratified by tumour type for comparison. The second objective is comparing ctDNA detection in CSF and blood plasma samples. This will involve observing the unique and shared mutations across sample types, and ultimately summarizing findings in a concordance table. From the table, test performance metrics such as sensitivity and specificity will also be derived. The third objective evaluates the feasibility of proteomic analysis and will be measured by the proportion of CSF samples that yield sufficient protein concentrations. The mean number of proteins detected per samples and any commonalities will be reported. All statistical analysis will be conducted using Excel and R. Given the exploratory nature of the study, graphical illustrations and plots will be emphasized over hypothesis testing with p-value.

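### The primary proportion is defined per patient but calculated per CSF sample, and the re-enrolment rule makes the two differ

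*Protocol*

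**What the plan says.** The Protocol defines the primary quantity per patient in three places. Research question 1 in the Synopsis asks what proportion of patients in each cohort have positive CSF markers. The primary endpoint is "Proportion of eligible patients with positive CSF cytology, positive ctDNA, and positive CTCs". The primary objective in Section 1 begins "To estimate the proportion of patients with solid tumours and CNS metastases" and extends to Cohort C.

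Section 7 (Planned Statistical Analysis) gives the calculation for that objective: "binary data will be analyzed to determine the proportion of positive CSF samples from the total number of samples collected". These proportions are then broken down by tumour type.

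Two further statements decide whether samples and patients can differ in number. The Synopsis describes the intervention as "One-time CSF collective via lumbar puncture or Ommaya reservoir", which means one sample per enrolment. Inclusion criterion 5 adds: "Patients who previously enrolled in the study but for whom CSF biomarkers were negative can re-enroll later", with CNS progression as the example. Each cohort is planned at 20 patients (Sections 3 and Synopsis), and recruitment lasts 12 months (Synopsis, Time Target).

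The Protocol does not say whether a re-enrolled patient counts once or twice, which result counts, which cohort the second sample joins, or whether the 20 are distinct people or enrolments.

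**The concern.** With one sample per patient, dividing by samples would be a loose way of dividing by patients. The re-enrolment rule removes that equivalence. A second sample can arise only through re-enrolment, and the Protocol offers re-enrolment to patients whose earlier result was negative. The number of units in the denominator therefore depends on the outcome being estimated.

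The study is purely one of estimation, so the primary proportion is its main result. As written, the same data can give three figures: the proportion positive at first sample, the proportion ever positive, and the proportion of samples positive. Section 7 prescribes the third, which is not the stated endpoint. If the unit is chosen after the results are known, the choice also settles the answer.

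**Working it through.** The Protocol states no expected positivity, re-enrolment rate or precision target, so there is no figure of its own to reproduce. The inputs are as follows.

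- From the Protocol: 20 patients per cohort; one sample per enrolment; re-enrolment open to patients with negative CSF biomarkers.
- Assumed: first-sample positivity 40%, so 8 positive and 12 negative; R negatives return to the same cohort; a proportion q of the repeat samples is positive, with q from 0.10 to 0.80. Each sample is treated as simply positive or negative.

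Formulas (expected values):

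- First-sample, per patient: 8/20 = 40%, whatever R and q are.
- Ever positive, per patient: (8 + Rq)/20.
- Per sample, as in Section 7: (8 + Rq)/(20 + R).

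| R | q | Per sample | Ever positive |
|---|---|---|---|
| 0 | – | 8/20 = 40.0% | 8/20 = 40% |
| 2 | 0.10 | 8.2/22 = 37.3% | 8.2/20 = 41% |
| 2 | 0.80 | 9.6/22 = 43.6% | 9.6/20 = 48% |
| 6 | 0.10 | 8.6/26 = 33.1% | 8.6/20 = 43% |
| 6 | 0.80 | 12.8/26 = 49.2% | 12.8/20 = 64% |
| 12 (upper bound) | 0.10 | 9.2/32 = 28.8% | 9.2/20 = 46% |
| 12 (upper bound) | 0.80 | 17.6/32 = 55.0% | 17.6/20 = 88% |

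Three things follow.

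1. The per-sample figure equals the first-sample proportion only if R = 0 or q = 0.40. Repeat negatives pull it down, and positives at progression push it up.
2. The per-sample and ever-positive figures share a numerator but divide by 20 + R and by 20. They differ whenever anyone returns and any sample is positive.
3. Other starting values give the same pattern. With 6 of 20 positive (30%) and two returns, the per-sample figure runs from 6/22 = 27.3% to 8/22 = 36.4%. With seven returns it runs from 6/27 = 22.2% to 13/27 = 48.1%.

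The table applies to a patient who re-enters the same cohort. A Cohort B patient who re-enrols with leptomeningeal disease would fit Cohort A. Each cohort then holds one sample from that patient, and per-sample and per-patient proportions agree within each cohort. Tumour type does not change, however, so the patient counts twice in any tumour-type stratum or total pooled across cohorts.

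The meaning of the 20 matters too. If it counts enrolments, six re-enrolments within one cohort leave 20 − 6 = 14 distinct patients.

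**The case against.** The strongest reply is that this is a small wording mismatch in a single-centre, exploratory feasibility study with no hypothesis test, power target or decision threshold. Re-enrolment may be rare. Recruitment lasts 12 months, and the Background gives median survival with leptomeningeal disease as 6–8 weeks untreated and 3–6 months treated. With two returns the shift from 40% is under 4 percentage points. In the 30% example, the two-return range of 27.3% to 36.4% lies well inside the exact 95% interval for 6/20, which is 11.9% to 54.3%. All of this stands, and it limits both the severity and the likely size. It does not remove the contradiction: the Protocol fixes a numerator and denominator that do not match its own endpoint, and nothing in it reconciles them.

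A reader might also infer more than the text supports:

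- *That repeat samples are analysed as independent and the intervals are wrong.* Section 7 states no interval, variance or independence assumption.
- *That a comparison between cohorts is distorted.* Cohort C is called a control group, but the Synopsis lists comparison as not applicable, and Section 7 compares by tumour type.
- *That positive patients are expressly barred from returning.* The Protocol never says so. This is an inference, though a reasonable one, from a permission that names negatives alone.
- *That ignoring failed collections is an error in itself.* Handling of non-evaluable samples is commonly left to a statistical analysis plan, which is not at hand.

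**Conclusion.** Wrong as written. Section 7 calculates a proportion of samples for an endpoint defined three times as a proportion of patients, and the re-enrolment rule ties the extra samples to a negative first result.

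The size is unknown because the Protocol gives no re-enrolment rate. Under the assumed 40% first-sample positivity and repeat positivity of 10% to 80%, the gap is zero with no returns, up to about 4 points with two and up to about 9 points with six, in either direction. Full re-enrolment is an upper bound and not a likely case. A claim that the estimate is biased upward, or by a large amount, is not supported. For a patient who changes cohort, the problem is confined to tumour-type strata and totals that pool the cohorts.

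This should be corrected before results are seen, but given the exploratory feasibility design it is a correction of moderate weight.

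**What to change.** In Section 7, replace the sentence on the first objective with: *the proportion of unique patients with a positive result, using the first-enrolment sample, in the cohort assigned at first enrolment; the denominator is patients with an evaluable first sample, with the number enrolled and the number not evaluable reported alongside.* An evaluable denominator is preferable to all enrolled patients, because the latter would count each failed collection as non-positive.

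Report re-enrolment samples separately, as paired first and second results. State beside inclusion criterion 5 that the target of 20 per cohort counts unique patients.

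The cost is wording only, with no extra samples or procedures. The downside is that re-enrolled patients no longer help to fill a cohort, including Cohort A, whose condition the Background describes as rare. Classifying by CNS status at sampling, with one result per patient per cohort, is a defensible alternative. It would have to be written down in advance, with a rule for counting each patient once in pooled and tumour-type figures.

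### Section 7 splits the primary proportion by tumour type and never mentions Cohorts A, B and C, so as written it does not give the by-cohort proportions that the research questions ask for

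*Protocol*

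**What the plan says.** **What is asked.** The Study Synopsis (Research Questions, item 1) asks, "in each of three pre-defined cohorts (A, B, C), what proportion of patients have a positive cytology", with ctDNA and CTCs alongside cytology. Questions 2 and 3 are also put for each cohort. Section 1 describes the population of the primary objective by cohort membership: "either meeting criteria for Cohort A or B), or no CNS metastases (Cohort C". Its first secondary objective reads "The concordance of mutations identified based on ctDNA profiling in the CSF and blood plasma in each of three cohorts (A, B, C", and the proteomic objective is likewise by cohort. Section 3 recruits 20 patients to each cohort and says that Cohort C "will be recruited as a control group".

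**What is planned.** For the first objective, Section 7 (Planned Statistical Analysis) will determine "the proportion of positive CSF samples from the total number of samples collected". The next sentence reads: "These proportions will then be stratified by tumour type for comparison". The section goes on to a CSF-plasma concordance table for objective 2 and to the share of samples with enough protein for objective 3. The cohorts appear nowhere in Section 7.

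**The endpoint line.** The primary endpoint in the Synopsis is "Proportion of eligible patients with positive CSF cytology, positive ctDNA, and positive CTCs". It counts patients but names no cohort.

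**The concern.** The protocol asks its question at one level and fixes its analysis at another. The cohorts are defined by CNS disease status: leptomeningeal disease, parenchymal brain metastases only, or neither. Marker positivity in each of these groups is what the study sets out to learn. A proportion over all samples averages the three groups, and its value describes none of them unless they happen to agree. Splitting by tumour type gives smaller averages that can each mix all three groups.

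This is more than detail left to a statistical analysis plan. The protocol is not silent: it names a denominator and a stratification factor, and neither matches its primary question. An analysis plan that followed Section 7 would inherit the mismatch, and one that reported by cohort would have to depart from Section 7.

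**Working it through.** The protocol gives no precision target, sample-size derivation or expected positivity rate, so there is no figure of its own to reproduce. The check is on the text, with arithmetic as illustration. All positivity counts and numbers of tumour types below are assumptions.

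**1. Can tumour type stand for cohort?** No. Section 3 describes Cohort A as "20 patients with any malignant solid tumour with LMD either suspected on imaging and/or confirmed via CSF cytology will be recruited", and Cohorts B and C are equally open to any malignant solid tumour. The Background uses tumour type for the primary cancer. The two factors cross each other.

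**2. Can the overall proportion give back the cohort proportions?** Planned sizes (Section 3): 20 + 20 + 20 = 60. Overall proportion = (x_A + x_B + x_C) / 60. Exact 95% limits for x out of n (Clopper-Pearson) are the 2.5% point of Beta(x, n − x + 1) and the 97.5% point of Beta(x + 1, n − x).

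| Assumed positives A / B / C | Overall (95% CI) | A (95% CI) | B (95% CI) | C (95% CI) |
|---|---|---|---|---|
| 16 / 6 / 2 | 24/60 = 40% (27.6–53.5) | 80% (56.3–94.3) | 30% (11.9–54.3) | 10% (1.2–31.7) |
| 10 / 8 / 6 | 24/60 = 40% (27.6–53.5) | 50% (27.2–72.8) | 40% (19.1–63.9) | 30% (11.9–54.3) |
| 8 / 8 / 8 | 24/60 = 40% (27.6–53.5) | 40% (19.1–63.9) | 40% (19.1–63.9) | 40% (19.1–63.9) |

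A steep gradient, a mild one and none at all give the same overall result. In the first row, 40% lies below the interval for Cohort A and above that for Cohort C.

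**3. Do tumour-type strata repair this?** With an assumed 3 to 8 tumour types, a stratum averages 60/3 = 20 down to 60/8 = 7.5 patients. Each stratum can hold patients from all three cohorts, so the problem in step 2 recurs inside each.

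**4. Patients or samples?** The research question and the endpoint count patients, while Section 7 counts samples. Inclusion criterion 5 lets a patient with negative CSF markers re-enrol later, for example on CNS progression. One patient can therefore give more than one sample, possibly in different cohorts. A patient who is negative first and positive on re-enrolment counts as 1 of 2 by sample and as one person by patient.

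**5. What does by-cohort reporting give?** With n = 20, the exact 95% CI is 0–16.8% for 0/20, 8.7–49.1% for 5/20 and 27.2–72.8% for 10/20. These intervals are wide but usable for a feasibility study, and they belong to the groups that the question names.

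**The case against.** **Pooling is inferred.** A reader might conclude that the plan commits to one figure pooled over cohorts and to tumour type as the only split. The text says neither. Section 7 introduces the analysis as serving the first objective, so it can be read back to a question already framed by cohort, with tumour type as a further split. That reading is possible and limits the claim. It does not remove it: the only denominator stated is all samples, the only factor named is tumour type, and the endpoint line names no cohort to settle the matter.

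**No between-cohort contrast is owed.** Because Cohort C is called a control group, a reader might infer that A–C and B–C differences are missing. The documents do not support that. The Synopsis marks the comparison item as not applicable, the primary objective is estimation, Section 7 puts plots ahead of tests, and no question, objective or endpoint asks for a difference.

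**Confounding and accrual are not shown.** A reader might say that tumour-type differences will merely reflect cohort, or that the overall figure will drift with recruitment. The first needs an uneven tumour mix across cohorts, which is plausible but not documented. The second needs a recruitment shortfall, whereas the plan is 20 per cohort and so equal weights. Neither is needed for the point.

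**Consequences are limited.** The study is small and descriptive, with no test or decision rule, and cohort membership is known from eligibility. By-cohort tables can be made from the same data. This stands, and it lowers the severity.

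**Conclusion.** The point holds in this form: Section 7 leaves out the cohort split that the research questions, the objectives and the 20/20/20 design call for, names a different stratifier, and counts samples where the question counts patients. Followed as written, it gives an overall proportion that cannot distinguish 80/30/10% from 40/40/40% across the cohorts, and tumour-type strata do not recover the difference. The counts are assumed, but the conclusion does not depend on them, since one total never determines its three parts. It does depend on reading the denominator as covering all cohorts, which is the plain sense of the sentence but is not spelled out. The severity is should-fix: nothing is lost irreversibly if the wording is corrected before analysis.

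**What to change.** In Section 7, state that:

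- the proportion positive for each marker (cytology, ctDNA, CTCs) is estimated per patient, separately within Cohorts A, B and C, with a 95% CI (exact, for example);
- a re-enrolled patient counts once per cohort, saying which of that patient's samples supplies the result;
- CSF-plasma concordance (objective 2) and proteomic feasibility (objective 3) are also reported by cohort;
- tumour type is a descriptive breakdown within cohort.

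Align the primary endpoint line in the Synopsis by adding the cohorts. Between-cohort differences with CIs are optional. If they are given, a patient who appears in two cohorts needs a mention.

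The cost is a few sentences, with no new data or patients. The downside is that the tumour-type comparison becomes description only: with an assumed five types, a cohort of 20 averages 20/5 = 4 patients per type, enough to list but not to compare.

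### Sensitivity and specificity are to be taken from a CSF-versus-plasma concordance table that has no reference standard, so their values depend on which fluid is treated as the truth

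*Protocol*

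**What the plan says.** The secondary endpoint in the Study Synopsis is "Concordance of mutations identified on CSF ctDNA with plasma ctDNA". Section 1 repeats it as an objective by cohort: "The concordance of mutations identified based on ctDNA profiling in the CSF and blood plasma in each of three cohorts". Both speak of concordance, and neither mentions diagnostic accuracy.

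Section 7 (Planned Statistical Analysis) introduces the analysis with "The second objective is comparing ctDNA detection in CSF and blood plasma samples" and describes the method: "This will involve observing the unique and shared mutations across sample types, and ultimately summarizing findings in a concordance table". The next sentence adds the accuracy metrics: "From the table, test performance metrics such as sensitivity and specificity will also be derived".

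The material collected is given under Intervention in the Synopsis: "One-time CSF collective via lumbar puncture or Ommaya reservoir and collection of concurrent plasma of peripheral blood (liquid biopsy". The Protocol describes no sequencing of tumour tissue. The one gold standard it mentions, in Section 2, is CSF analysis for diagnosing leptomeningeal disease. Section 7 (Planned Cytological Analysis) leaves the platform open, with next-generation sequencing and droplet digital PCR among the candidates.

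**The concern.** Sensitivity and specificity are conditional on a truth column. A table of CSF ctDNA against plasma ctDNA has none: it cross-classifies two index tests on fluids from different compartments. A mutation found in only one fluid may be a false call or a miss, or it may be a real mutation shed into that compartment alone. The table cannot tell these apart, and the accuracy labels force every discordant mutation into an error category.

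This matters because discordance is part of what the comparison is meant to describe. The Background hopes that "we may identify a novel mechanism to understand targetable mutations of CNS metastases". A real CSF-only mutation could bear on that aim, yet it would enter the accuracy figures as an error of one fluid or the other.

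At mutation level there is a second difficulty. The cell for mutations absent from both fluids is not observed as such. It is the number of loci assayed minus the mutations seen, so specificity depends on panel size, and the panel is not yet fixed.

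**Working it through.** The Protocol states no sensitivity, specificity or agreement figure, so there is nothing to reproduce. All counts below are assumptions chosen for illustration.

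**Notation.** s = shared mutations, c = CSF-only, p = plasma-only, K = loci assayed, n = K − s − c − p = loci mutated in neither fluid.

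- Plasma as reference: CSF sensitivity = s/(s + p); CSF specificity = n/(n + c).
- CSF as reference: plasma sensitivity = s/(s + c); plasma specificity = n/(n + p).

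**Step 1: which error each discordant mutation becomes.**

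| Real mutation found in | Plasma as reference | CSF as reference |
|---|---|---|
| CSF only | CSF false positive | plasma false negative |
| Plasma only | CSF false negative | plasma false positive |

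Under either choice, both kinds of discordant mutation count as errors, even if every one is real.

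**Step 2: mutation-level table with s = 3, c = 2, p = 3.** Sensitivity is 3/(3 + 3) = 50% for CSF against plasma and 3/(3 + 2) = 60% for plasma against CSF. Specificity for three values of K:

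| K | n = K − 8 | CSF specificity, plasma as reference | Plasma specificity, CSF as reference |
|---|---|---|---|
| 8 (only the observed mutations) | 0 | 0/2 = 0% | 0/3 = 0% |
| 50 | 42 | 42/44 = 95.5% | 42/45 = 93.3% |
| 500 | 492 | 492/494 = 99.6% | 492/495 = 99.4% |

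The observed mutations are the same in every row; only the panel size differs.

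**Step 3: other assumed counts.** With s = 2, c = 4, p = 2, CSF specificity against plasma is 2/6 = 33.3% at K = 10 and 492/496 = 99.2% at K = 500. Over four assumed sets of (s, c, p), namely (3, 2, 2), (2, 4, 2), (4, 1, 1) and (1, 5, 1), it runs from 0.33–0.80 at K = 10 to 0.990–0.998 at K = 500. The pattern is not peculiar to one set of counts.

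**Step 4: patient-level table.** Take one cohort of 20 patients with 6 positive in both fluids, 8 in CSF only, 2 in plasma only and 4 in neither.

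- Plasma as reference: sensitivity 6/8 = 75.0%, specificity 4/12 = 33.3%.
- CSF as reference: sensitivity 6/14 = 42.9%, specificity 4/6 = 66.7%.

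The panel denominator has gone. The dependence on the reference has not.

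**Step 5: agreement measures on the same data.** For the counts in Step 2, the shared fraction is 3/8 = 37.5%, the CSF-only fraction 2/8 = 25.0% and the plasma-only fraction 3/8 = 37.5%. None of them uses n, so they are the same at every K, and none requires a fluid to be called the truth.

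**The case against.** The strongest defence has three parts.

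*The metrics are secondary to the table.* The endpoint and objective are concordance. Accuracy appears in one added sentence, and no stated decision, test or sample size rests on it. The study calls itself exploratory and favours plots over p-values. The unique and shared mutations are to be summarised anyway, so CSF-only findings stay visible. This stands, and it limits the severity.

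*Reference, unit and clustering can be left to an analysis plan.* As a general matter they can, and their absence alone would not be a finding. But the Protocol does fix that the accuracy metrics come from this table. An analysis plan could repair that only by departing from the sentence or by bringing in a reference that the table does not contain.

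*Agreement is partly a relabelling.* At patient level, the share of plasma-positive patients who are also CSF-positive equals CSF sensitivity against plasma (6/8 in Step 4). The arithmetic is indeed the same. What changes is that both directions are reported and that neither fluid's discordant results are called errors.

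A reader might infer more than the documents support:

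- That CSF-only mutations will be scored as CSF false positives, to the detriment of CSF. This follows only if plasma is the reference, which the Protocol does not say. With CSF as reference, they count against plasma.
- That specificity must depend on the panel. This needs the mutation as the unit. The reference to unique and shared mutations suggests that unit, but the phrase about ctDNA detection leaves a patient-level table possible.
- That the Background promises mutations private to the CNS. Its contrast is with surgical resection by craniotomy, not with plasma.
- That double-negative pairs will be common in Cohort C and inflate agreement. The Protocol gives no detection rates, and these patients have metastatic disease.

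**Conclusion.** The concern holds in this form: the Protocol takes sensitivity and specificity from a table with no reference standard. The resulting figures depend on which fluid is called the truth, and they count real compartment-specific mutations as errors. In the assumed example sensitivity is 50% or 60% according to that choice. In the assumed patient-level table the sensitivity/specificity pair is 75.0%/33.3% or 42.9%/66.7%. If the unit is the mutation, specificity can also lie anywhere from 0% to 99.6% on the same observed mutations, according to the number of loci assayed.

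These sizes rest on assumed counts; the Protocol gives none. The reference problem does not depend on them, except that the two sensitivities coincide when CSF-only and plasma-only counts happen to be equal. The panel problem is conditional on a mutation-level table.

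This should be fixed before analysis, since it affects how the only secondary endpoint is reported. It does not threaten the study, because the concordance endpoint itself is sound and descriptive.

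**What to change.** Delete sensitivity and specificity from the analysis of this table. In Section 7, state instead that the following will be reported for each cohort:

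1. **Patient level.** The full 2x2 counts of ctDNA detection in CSF and plasma, with agreement in both directions: the share of CSF-positive patients who are also plasma-positive, and the share of plasma-positive patients who are also CSF-positive.
2. **Mutation level.** Among patients with at least one mutation in either fluid, the per-patient shared, CSF-only and plasma-only fractions, each with s + c + p as denominator. Summarise them across patients with a bootstrap interval that resamples patients, so that several mutations from one patient are not treated as independent. With at most 20 planned patients per cohort the intervals will be rough and should be presented as descriptive.

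Add that accuracy terms will be used only if an independent reference and the unit of analysis are named beforehand.

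The cost is a change of wording and slightly more analysis in R, which the Protocol already plans to use. No patients, samples or procedures are added. Sequencing the stored buffy coat, or using tumour molecular reports, is not part of this fix: the first would be an extra assay, and the Protocol does not mention the second.
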